## 9.4 Safety Analyses

### 9.4.1 Trial Drug Exposure

Descriptive statistics will be summarized for cell count, cell viability, endotoxin completion status, and 14-day sterility testing status by BMAC, UCT and SVF treatment arms. The treatment data for BMAC, UCT, SVF and CSI arms will be provided in four separate data listings. Cell count and cell viability data will also be included in the listings for BMAC, UCT and SVF treatment arms.

### 9.4.2 Adverse Events

All adverse events (AEs) and serious adverse events (SAEs) will be classified by System Organ Class (SOC) and Preferred Term (PT) according to the Medical Dictionary of Regulatory Activities (MedDRA) version 21.1 for the safety population. The number and percentage of subjects reporting AEs, as well as the number of events, in each treatment group will be tabulated by SOC and PT; by SOC, PT, and maximum severity; and in relationship to study treatment, SOC and PT. If a subject has multiple occurrences of the same SOC and PT, then the subject will be counted only once for the SOC and PT using the most severe occurrence for the summarization by maximum severity. Presentation by SOC and PT will display SOC sorted alphabetically and PT by descending frequency within SOC.

### 9.4.3 Continuous Monitoring of Specific Adverse Events

In addition, the incidence of specific safety related events of concern will be continuously monitored separately in each treatment arm at each center throughout the study to determine if any of their observed subject-based incidence rates exceed a threshold incidence rate of concern pre-specified for each particular event (for example infection and allergic reaction related to study harvest procedure and/or knee injection).

These rules will be implemented by Advanced Clinical continuously monitoring the occurrence of any events to determine if the currently observed rate of each exceeds the corresponding threshold rate of concern with a pre-specified level of confidence. The stopping rule will be considered to be met if the lower 95% confidence limit on the observed incidence rate exceeds the corresponding threshold level of concern for that event. If any stopping rule is met, enrollment and randomization will be suspended pending expedited DSMB review.

The following table describes the minimum number of events out of the selected numbers of subjects randomized to each treatment arm at each site

which, if equaled or exceeded, would satisfy the stopping rule for each event of concern.

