### 1.1 Synopsis

Title of Study	Randomized multicenter phase 3 single-blind trial comparing the efficacy of corticosteroid control to mesenchymal stem cell preparations from autologous bone marrow concentrate (BMAC), adipose derived stem cells in the form of Stromal Vascular Fraction (SVF), and third party human mesenchymal stem cells manufactured from umbilical cord tissue (UCT) for the treatment of unilateral Knee Osteoarthritis (OA).
Study Objectives	To identify a superior source of stem cells for the treatment of osteoarthritis and validate its advantages over corticosteroid injections as traditional gold standard treatment. The primary efficacy co-outcomes are: a change in the visual analog score (VAS) pain score and a change in the pain subsection of the knee injury and osteoarthritis outcome (KOOS) score. Secondary endpoints include total KOOS score, Magnetic Resonance Imaging (MRI) and additional patient reported outcomes (PROs).
Study Design	Multicenter prospective single-blinded randomized controlled clinical trial. The study will include a parallel design using a blocked central randomization scheme of 1:1:1:1. Subjects will be allocated to three different arms with a 3:1 assignment. Autologous bone marrow concentrate (n=120): corticosteroid (n=40), umbilical cord tissue (n=120): corticosteroid (n=40), and adipose derived SVF (n=120): corticosteroid (n=40).

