### **6.2.2 Implementation of Randomization and Blinding**

Subjects randomized to Arm 1 or Arm 2 will undergo a procedure (bone marrow aspiration or liposuction) but will only receive one of the possible injections. For instance, subjects randomized to the control portion of Arm 1 will undergo a bone marrow aspiration but will receive a blinded corticosteroid injection. The bone marrow aspirate will still be processed and used to help quantify cell characteristics. Subjects randomized to Arm 3 will not undergo the procedures mentioned above. They will be blinded and receive either the stem cell injection or the corticosteroid injection.

Four hundred eighty subjects will be randomly assigned to treatment in this multicenter trial. Subjects at each clinical site will be randomized to ensure the trial is single-blind with a 1:1 allocation ratio across the four treatment groups.

One hundred twenty subjects will be randomized at each of 4 clinical sites. Arm 1: Forty subjects will be randomized with a 3:1 allocation ratio (bone marrow derived MSCs versus corticosteroid injection; 30:10). This same implementation plan will be used to randomize 40 subjects to Arm 2 (adipose derived MSCs versus corticosteroid injection) with a 3:1 allocation ratio and to randomize 40 subjects to Arm 3 (umbilical cord tissue MSCs versus corticosteroid injection) with a 3:1 allocation ratio.

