#### **9.2 Sample Size Determination**

The total estimated sample size for the proposed intention-to treat, parallel-group, multicenter, randomized, controlled trial is 480 subjects. The primary endpoints are Visual Analog Scale (VAS) pain score and the pain subsection of the Knee Injury and Osteoarthritis Outcomes (KOOS). The sample size calculations are based on improvements (from baseline to 1-year) in the visual analog scale (VAS) pain score and total KOOS. Total KOOS was used as a proxy and should ensure that the study is amply powered.

Assuming a decline of 1 point on average in pain in the Control arm (corticosteroids) and a decline on average of 2.5 points in a treatment arm (mesenchymal stem cells) and an estimated standard deviation on change of 3.5, the proposed sample sizes (n=121 subjects

per group or 484 total subjects) will provide 91% power to detect a difference on change of 1.5 points at the two-sided 5% significance level if the true difference between treatment groups is 1.5 points (two-sided two-sample equal variance t-test).

Assuming an increase of 10 points on average in total KOOS in the Control arm (corticosteroids) and an increase on average of 20 points in a treatment arm (mesenchymal stem cells) and an estimated standard deviation on change of 20, the proposed sample sizes (n=121 subjects per group or 484 total subjects) will provide 97% power to detect a difference on change of 10 points at the two-sided 5% significance level if the true difference between treatment groups is 10 points (two-sided two-sample equal variance t-test).

Each of the four participating sites will accrue 30 subjects to each of the 4 treatment groups. Cohort retention is expected to be 90% at 1-year.

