### **9.3.3 Efficacy Analyses across Subgroups**

The heterogeneity of treatment effects across age, sex, and ethnicity will be evaluated using a statistical test for interaction terms. Specifically, effects of treatment in subgroups will be determined by including the additional interaction terms between treatment and the three subgroups (age, sex, and ethnicity) in the repeated measures model described above for the eight efficacy variables.

The following variables will be treated as categorical variables in all of the linear mixed models.

- Treatment arms: CSI (reference), BMAC, ADP, UCT
- Age:  $\leq 65$  (reference) vs.  $>65$
- Sex: female vs male (reference)

- Ethnicity: Hispanic vs non-Hispanic
- Time: 0, 1, 2, 3, 4, 5 representing baseline and 1, 3, 6, 9 and 12 months follow-up visits

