**Table 1. Study Termination Rules for Infection and Allergic Reaction:**

Minimum Number of Subjects with Events Meeting Stopping Rule for Infection and Allergic Reaction (infections and/or allergic reactions must be related to the harvesting procedure and/or knee injection) for Selected Numbers of Subjects Randomized Per Treatment Arm at each Center Using a Threshold Incidence Rate of Concern of 10%

Number of Subjects with Event	Number of Randomized Subjects Total	Incidence Rate	Lower 95% Confidence Limit, Wilson score method
1	5	20%	4%
2	5	40%	12%
1	10	10%	2%
2	10	20%	6%
3	10	30%	11%
4	10	40%	17%
4	20	20%	8%
5	20	25%	11%
6	20	30%	15%
5	30	17%	7%
6	30	20%	10%
7	30	23%	12%

Examples above illustrate threshold number of events that exceed the stopping rule (highlighted in bold); non-highlighted entries illustrate the observed incidence rate and the lower 95% confidence limit that does not exceed the stopping rule threshold of 10%

For each treatment arm at each center: if the lower confidence interval for the estimated infection and allergic reaction rate is 10% or higher, then enrollment and randomization will be suspended pending DSMB review. Infection and/or allergic reactions must be related to the harvesting procedure and/or knee injection.

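### Section 9.4.3 appears to count harvest-related infections by injected product, so harvested steroid controls sit in a CSI group where a one-procedure problem is diluted to a third; site-level loss is modest

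*Combined protocol and SAP*

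**What the plan says.** Section 9.4.3 has the specified events "continuously monitored separately in each treatment arm at each center throughout the study". The rule is met when the lower 95% limit of the observed rate passes 10%. The note under Table 1 sets the event definition: "Infection and/or allergic reactions must be related to the harvesting procedure and/or knee injection". Harvest and injection events thus enter one count.

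Three places bear on what an arm is in section 9:
- Section 9.3.3 lists "Treatment arms: CSI (reference), BMAC, ADP, UCT".
- Section 9.4.1 says "The treatment data for BMAC, UCT, SVF and CSI arms will be provided in four separate data listings".
- Section 9.2 says "Each of the four participating sites will accrue 30 subjects to each of the 4 treatment groups", and Table 1 stops at 30.

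Sections 4.1 and 6.2.2 use the word differently. There, Arms 1, 2 and 3 are the marrow, adipose and cord strata, each with cell and steroid subjects and 40 per site.

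On exposure, section 6.2.2 says that "subjects randomized to the control portion of Arm 1 will undergo a bone marrow aspiration but will receive a blinded corticosteroid injection". Section 6.0 has lipoplasty done in everyone in Arm 2. Arm 3 subjects have no harvest. Section 9.4.4 also compares infection by treatment arm, with harvest site and knee combined.

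**The concern.** The risk of a harvest infection follows the procedure a subject undergoes, while the monitoring group follows the product injected. The two coincide in the BMAC, SVF and UCT groups but not in CSI. Across the trial 40 + 40 = 80 of the 120 CSI subjects are harvested without having the product injected; their harvest serves blinding and cell characterization. Any harvest infections they have are averaged over people who never had that procedure, and are not added to the infections from the same procedure at the same site in the matching cell group. A per-centre rule is the natural place to notice that one site has trouble with aspiration or liposuction, and no tally in 9.4.3 or 9.4.4 is kept by procedure.

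**Working it through.** **1. Reproducing Table 1.** Two-sided 95% Wilson lower limit with z = 1.96:

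L = [p + z²/(2n) − z·√(p(1−p)/n + z²/(4n²))] / (1 + z²/n), where p = x/n.

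All twelve rows reproduce to the printed whole percent, in order: 3.62, 11.76, 1.79, 5.67, 10.78, 16.82, 8.07, 11.19, 14.55, 7.34, 9.51, 11.79. The 6/30 row is bolded as a trigger, but its limit is 9.51% and reaches 10% only by rounding. Results are therefore given on two readings: strict (limit above 10%, so 7/30) and rounded (as in Table 1, so 6/30).

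**2. Who is in each group at one site** (sections 6.0, 6.2.2 and 9.2)

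| Product group | n | Aspirated | Liposuctioned | No harvest |
|---|---|---|---|---|
| BMAC | 30 | 30 | 0 | 0 |
| SVF | 30 | 0 | 30 | 0 |
| UCT | 30 | 0 | 0 | 30 |
| CSI | 30 | 10 | 10 | 10 |
| Total | 120 | 40 | 40 | 40 |

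**3. Dilution in CSI.** A rate p from one procedure appears as p × 10/30 = p/3. Four infections in a site's 10 liposuctioned controls have a lower limit of 16.8% as 4/10, but are counted as 4/30, limit 5.3%. With no other CSI events, 7 of those 10 (strict) or 6 of 10 (rounded) must be infected to trip the rule at full accrual.

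**4. Chance that the CSI group trips, single look at full accrual.** True rates are assumptions; other CSI subjects are taken to have no events. X is Binomial(10, p).

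| True rate | P(X ≥ 7), strict | P(X ≥ 6), rounded | P(X ≥ 3), the 10 exposed judged alone |
|---|---|---|---|
| 20% | 0.1% | 0.6% | 32% |
| 25% | 0.4% | 2.0% | 47% |

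Repeated looks at Table 1's sample sizes raise the CSI chance at a true 20% only to about 4.5%.

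**5. Chance that the site trips at all.** By product means that the matching cell group or CSI trips. By procedure means all 40 exposed subjects together, with a trigger of 8/40 (limit 10.50%; 7/40 gives 8.75%).

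| Looks and reading | True rate | By product | By procedure |
|---|---|---|---|
| Final look, strict | 20% | 39.4% | 56.3% |
| Final look, rounded | 20% | 57.5% | 56.3% |
| At 5, 10, 20, 30 (and 40), bolded counts | 20% | 67.0% | 70.7% |
| Same | 25% | 85.6% | 89.0% |
| Same | 30% | 95.0% | 97.0% |
| Every subject from n = 5, strict | 20% | about 67% | about 73% |
| Every subject from n = 5, rounded | 20% | about 72% | about 76% |

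The rows with repeated looks are simulations with independent events. The assumed order of entry moves them by a point or two: random placement of one control in each block of four gave 66% against 72% on the strict reading.

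**6. Running both tallies, a look after every subject.** The site trips if either tally does.

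| True rate | Strict: by product → both | Rounded: by product → both |
|---|---|---|
| 20% | 67% → 77% | 72% → 81% |
| 10% | 18% → 23% | 22% → 26% |
| 5% | 3% → 4% | 5% → 6% |

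**The case against.** **The term may mean something else.** The list in 9.3.3 is introduced for the linear mixed models, and Table 1 gives only selected sample sizes. If 9.4.3 meant Arms 1 to 3, harvest events would already be pooled by procedure. This cannot be excluded, but 9.4.1 names CSI as its own arm within the safety section, and the table ends exactly at the per-site size of a product group. On the other reading the table would stop short of 40. Either way the term needs defining.

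**The size is easily overstated.** A reader might infer that site-level detection at a true 20% drops from 56% to 39%. That needs a 7/30 trigger, although Table 1 bolds 6/30, and a single look at the end, although the rule is continuous. With 6/30 the final-look difference vanishes (57.5% against 56.3%), and with repeated looks it is roughly 4 to 6 points.

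**Striking splits are not typical.** Take 20 liposuctions (15 SVF, 5 controls; 15 CSI subjects in all) and 5 infections. Split 3:2, they trip neither group (3/15, limit 7.1%; 2/15, 3.7%), while 5/20 gives 11.2%. By the hypergeometric distribution that split has probability 29%. With probability 63% SVF has at least 4, and 4/15 (10.9%) already trips.

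**Other safeguards exist.** Any potentially related SAE halts enrolment whatever the group (section 4.5). AEs are listed per site for the medical monitor and DSMB (section 8.4.5), and harvest sites are inspected at days 7 and 30 in controls too. It would be wrong to infer that harvest infections go unseen. This cover is real but partial: non-serious infections then rest on judgement and not on the pre-specified rule.

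The documents also do not say that the same operators harvest cell and control subjects, so the point does not rely on that.

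**Conclusion.** The concern holds as a mismatch between monitoring group and hazard, with a modest effect at site level. On the most natural reading of section 9, the rule runs by injected product. The CSI group is then nearly blind to a problem with one procedure: 0.1% or 0.6% at a final look and about 4.5% with repeated looks, at a true 20%. The BMAC and SVF groups are undiluted and lose only the 10 controls, a quarter of the 40 exposed to each procedure, so most site problems would still be caught there. These results assume true rates of 5% to 30%, independent events and no events among CSI subjects not exposed to the procedure in question; the documents give no expected event rate at the sites. The stronger inference, that the plan misses a large share of harvest problems, is not supported.

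**What to change.** In section 9.4.3:

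1. State whether *treatment arm* means the four product groups or Arms 1 to 3, and use one term throughout.
2. Keep the existing combined harvest-and/or-injection count by product. It should not be replaced by separate counts. Three harvest and three knee infections in different SVF subjects now make 6/30, a bolded trigger; split, with no control events, they become 3/40 (limit 2.6%) and 3/30 (3.5%), and neither trips.
3. Add a second tally per site of harvest-related events by procedure undergone: all Arm 1 aspirations, and all Arm 2 liposuctions, with cell and CSI subjects together.
4. Extend Table 1 to n = 40 (8 events, limit 10.5%), and reconcile the 6/30 row with the wording of the rule.

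The cost is wording and one more CRO tally; relatedness to harvest or injection is already part of the event definition. Suspensions for DSMB review become somewhat more frequent per procedure per site: by about 4 to 5 percentage points at a true 10% and about 1 point at a true 5%.

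### The 95% confidence attached to the Section 9.4.3 suspension rule holds for one look, not for continuous checking in 16 arm-by-centre cells; the boundary at 30 subjects also needs reconciling

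*Combined protocol and SAP*

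**What the plan says.** Section 9.4.3 has the events "continuously monitored separately in each treatment arm at each center throughout the study". The stated purpose is to determine if "the currently observed rate of each exceeds the corresponding threshold rate of concern with a pre-specified level of confidence". The criterion follows: "The stopping rule will be considered to be met if the lower 95% confidence limit on the observed incidence rate exceeds" the threshold for that event. Meeting it suspends enrolment and randomization until an expedited DSMB review.

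Table 1 sets the threshold at 10%, heads its limit column "Lower 95% Confidence Limit, Wilson score method" and uses randomized subjects as the denominator. It gives examples at 5, 10, 20 and 30 subjects. Under the table the trigger is worded differently: "if the lower confidence interval for the estimated infection and allergic reaction rate is 10% or higher".

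Section 9.3.3 names four treatments ("Treatment arms: CSI (reference), BMAC, ADP, UCT"), and Section 9.2 has each of four sites accrue 30 subjects to each. The section states no minimum cell size, no allowance for repeated looks or for the number of cells, and no operating characteristics.

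**The concern.** A 95% limit computed once, at a size fixed in advance, exceeds the true rate about 2.5% of the time. If it is recomputed as each subject is added and acted on the first time it passes 10%, the chance of ever passing is larger. It is larger again when any of 16 cells can trigger. The text links its confidence statement to a continuously applied rule without saying so.

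At stake is how the DSMB reads a trigger. Taken at face value, it is strong evidence that a product at a site has an event rate above 10%. If triggers are common when the rate is at or below 10%, that reading is wrong, and enrolment may pause for a chance pattern in a small cell. A DSMB that does not know the rule's real behaviour cannot weigh a trigger properly.

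**Working it through.** **Inputs.** Lower 95% limit and continuous checking: Section 9.4.3. Wilson method, 10% threshold and randomized denominator: Table 1. Four treatments: Section 9.3.3. Four sites with 30 subjects per treatment: Section 9.2. True event rate: not given in the documents, so a range is shown.

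**Reproducing Table 1.** With p = x/n and z = 1.96,

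L(x,n) = [p + z²/(2n) − z·√(p(1−p)/n + z²/(4n²))] / (1 + z²/n).

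All 12 rows reproduce to the nearest percent: 1/5 3.62, 2/5 11.76, 1/10 1.79, 2/10 5.67, 3/10 10.78, 4/10 16.82, 4/20 8.07, 5/20 11.19, 6/20 14.55, 5/30 7.34, 6/30 9.51, 7/30 11.79. A one-sided z of 1.645 does not fit (2/5 would be 14.3%), nor does Clopper-Pearson (5.3%).

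**The row 6/30.** L = [0.2 + 0.0640 − 1.96·√(0.005333 + 0.001067)] / 1.1281 = 0.1072/1.1281 = 0.0951. The table prints 10% in bold. Unrounded, 9.51% neither exceeds 10% nor is 10% or higher. Rounded, it satisfies the second wording but not the first. The unrounded boundary at 30 is 7 events.

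**The smallest cells.** For 1/1, L = (1 + 1.9208 − 1.9208)/4.8416 = 20.65%, which meets the rule. For 1/2, L = 9.45%, which does not. The minimum number of events for n = 1 to 30 is 1,2,2,2,2,3,3,3,3,3,4,4,4,4,4,4,5,5,5,5,5,5,6,6,6,6,6,6,7,7.

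**Chance of a trigger.** Let q_n(x) be the probability of x events after n subjects with no trigger so far. Then q_n(x) = (1−r)·q_{n−1}(x) + r·q_{n−1}(x−1) for true rate r. At each look, probability at or beyond the boundary moves to the trigger probability c. For 16 independent cells with the same rate, the any-cell chance is 1 − (1−c)^16. A lag of k means that an event becomes known only after k further randomizations in that cell; all events are known at the end.

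| Looks | Per cell, true 10% | Any of 16, true 10% | Any of 16, true 5% | Any of 16, true 2% |
|---|---|---|---|---|
| One look at n = 30 | 2.6% | 34% | 0.9% | 0.0% |
| Continuous, no lag | 21.8% | 98% | 70% | 31% |
| Continuous, lag 1 | 13% | 90% | 31% | 4% |
| Continuous, lag 2 | 10% | 83% | 21% | 2.5% |
| n = 5, 10, 20, 30 only | 14% | 90% | 38% | 7% |

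Example: with no lag at 10%, 1 − (1 − 0.2177)^16 = 0.980. The per-cell chance at the threshold is about four to eight times the single-look value (10.4/2.6 = 4; 21.8/2.6 = 8.4).

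**Why lag matters.** The Schedule of Activities places randomization at screening, up to 30 days before Day 0, and the first follow-up is Day 7. Thirty subjects per cell over about 13 months (Section 4.3) is one randomization roughly every 13 × 30.4/30 ≈ 13 days. A lag of one or two is therefore plausible, and with any lag of at least one, 1/1 cannot trigger.

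**The case against.** A reader might infer that the rule fires on one event in a cell's first subject and so has about a 70% chance of a false suspension. The documents do not support stating that as fact:

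- The 70% needs every event to be known before the next randomization in the cell, which the visit timing makes unlikely. Much of it comes from 1/1: with looks starting at 5 subjects it is 41%.
- It also needs a true rate of 5% in every cell, which is an assumption. The 1-10% band in Section 2.3.1 is a broad risk category, not an expected rate of related infection or allergy. In the marrow-aspiration series in Section 2.2, all adverse events other than the 183 pain events amount to (325 − 183)/3012 = 4.7%.

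Other points in the plan's favour also stand. The limits in Table 1 are computed correctly, apart from how 6/30 is classified. The text does not explicitly claim error control over repeated looks or 16 cells. The action is a pause for review, Section 4.5 already halts enrolment for any potentially related serious event, and Section 4.3 allows three extra months. A cautious rule may be intended.

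None of this rescues the confidence statement. The comparison at a true 10% uses the plan's own threshold, so it needs no assumed expected rate, and it fails under every pattern of repeated looks examined. Table 1 calls its sizes selected examples, so they set no minimum; even looking only at those four sizes gives 14% per cell.

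**Conclusion.** The concern holds in a limited form. The confidence in Section 9.4.3 is a single-look property attached to a rule that is checked continuously. At a true rate of exactly 10%, a cell triggers with probability 10% to 22% instead of 2.6%, and at least one of 16 cells triggers with probability 83% to 98%. At an assumed 5%, the any-cell chance is 21% to 70%, with 70% as the no-lag upper limit. At 2% it is 2.5% to 31%.

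These figures assume independent cells with a common rate and full accrual of 30 per cell. Reading arm as Arms 1 to 3 gives 12 cells of 40 and 59% in place of 70%; the table's end at 30 favours 16 cells.

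The rule errs toward caution, so this is not a gap in subject protection. It is a misstatement of what a trigger shows, together with a boundary at 30 subjects that conflicts with both wordings of the rule.

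**What to change.** In Section 9.4.3:

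1. Replace the unqualified confidence statement with the rule's operating characteristics under continuous monitoring, per cell and for any of 16 cells, over a range of true rates and with the reporting-lag assumption stated. Say that a trigger prompts DSMB review and is not 95% evidence of a rate above 10%.
2. Print the boundary for every cell size from 1 to 30, so that the sponsor and DSMB decide explicitly whether one event in one subject is meant to trigger. Any minimum event count is theirs to set.
3. Reconcile the two wordings (above 10%, or at least 10%) with each other and with the bold row 6/30, and say whether limits are compared before or after rounding. Rounding matters: comparing rounded limits raises the no-lag any-cell figure at 5% from 70% to 74%.

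The 10% threshold and the expedited DSMB review are unchanged. The cost is a longer table and a less favourable statement of confidence.
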